RESPONSE: Aim 1: Determine the safety and feasibility of externally mounted magnetic devices for extended (> 1 week) home use for the management of early post-acute and chronic eyelid movement disorders. Aim 2: Collect preliminary data on the efficacy of external magnetic eye lid devices stemming from a variety of different pathologies.

OBJECTIVES

3) Your focused research question needs to be further refined into one or more study objectives. The study objective(s) should be single and quantifiable statement(s) that will allow you to answer your research question.

RESPONSE: Objective 1: Determine the safety and feasibility of externally mounted magnets for extended management of chronic eyelid movement disorders by measuring visual acuity and corneal and skin integrity and comfort over 8 weeks of wear.

HYPOTHESES

4a). Primary Hypothesis - Hypotheses are more specific than objectives and amenable to statistical evaluation. Your primary hypothesis is your statement of the hypothesized effect on the primary outcome measure. A hypothesis is worded very simply and written as 'testable' statements. Your experimental results will prove or disprove your hypothesis. Hypotheses are generally stated in the null form (H_0) as they have their basis in inferential statistics. Rejecting the null hypothesis increases our confidence, with a given level of probability, that there is a relationship between the variables being studied. However, a classic scientific hypothesis includes both a null and alternative (H_a) hypothesis.

**e.g. H_0 : Asthma prevalence rates are not different among children from low and high socioeconomic groups in Istanbul. H_a : Asthma prevalence rates are different among children from low and high socioeconomic groups in Istanbul.*

RESPONSE: Hypothesis: Externally mounted magnet systems will have a good safety profile defined as a mean decrease in visual acuity 1 line or less, high-mag photo documented skin-integrity rating better

than 2 (FDA industry scale), and no more than a two grade (NEI/Industry Workshop scale (Lemp, 1995)) worsening in superficial punctate keratitis on high mag photo-documented analysis.

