RESPONSE: Skin integrity scales, change in ocular surface staining rating, participant comfort and satisfaction rating, and change in visual acuity. Skin integrity will be analyzed by applying a likert-type rating system to a high-mag/high-resolution photo documented image of the subject's lid skin. The number of adverse events will also be reported, defined as incidents which require temporary or permanent suspension of the participant's involvement. These include any broken skin, decrease in visual acuity more than 2 lines, worsening of corneal rating of more than 1.5 points or other ocular surface ratings more than 2 points, and comfort rating lower than 5/10 (or 50cm on the 100cm visual analog scale).

7b). Secondary Outcome(s) - Secondary outcome(s) are measures of additional or less important research interest. They may include additional clinical, psychological, economic, or safety outcomes (e.g. treatment related side effects/adverse events). However, as these endpoints are not used to calculate study power and sample size it is often not possible to draw robust conclusions from the results.

RESPONSE: Video analysis of eyelid biomechanics to measure the completeness of eye closure and opening compared to 1) no device, 2) relative to the contralateral side (if normal), 3) relative to the ptosis crutch or external lid weights. The same paired comparisons will be performed for the clinician and participant rating scale data. 3) Cognitive score on the MoCA will be analyzed for relationship to length of time in the study and satisfaction rating scores).

STUDY PROCEDURES

8) In this section you need to clearly and comprehensively describe exactly what will happen to participants once they are enrolled in your study. Depending on the study it might include how potential participants will be approached, when they will be randomized, the frequency and duration of visits or whether they are expected to self-complete a daily diary at home, the duration of the study or follow-up, and any measurements taken at each visit (e.g. questionnaires, physical measurements, biological samples).

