spectacle mounted magnet may also be used for lagophthalmos (mounted within the inferior eye-wire to pull the upper lid down). In this scenario there is no lower lid array. **20 MINUTE TRIAL:** For both the ptosis and lagophthalmos magnet devices: If experimenter likert-type scale score is greater than or equal to 6 on the blink mechanics and efficacy and better than 8 on the skin integrity and the participant rated comfort is greater than or equal to 5/10 on likert-type or 50mm or better on a 100mm Visual Analog Scale and they express a desire to continue wearing the device, they will be offered participation in an extended 20 minute trial. This is followed by a repeat of the visual acuity, slit lamp exam, video and rating scale data collection. **EXTENDED 1-WEEK TRIAL:** Participants who have a successful 20 minute magnet device trial defined as an Examiner Rating Scale score of greater than or equal to 6 on the blink mechanics and efficacy, better than 8 on the skin integrity, participant rated comfort greater than or equal to 5/10 (or 50mm on a 100mm Visual Analog Scale), and express a desire to continue wearing the device will be offered participation in an extended 1-week trial. These cut-offs were based on observations during the pilot study at Spaulding (see manuscript attached) where patients who reported a desire to wear the device typically rated their comfort and satisfaction at this level or better. The PI or other trained study staff supervised by the PI will train the patient how to apply and remove the lid magnet; similar to what is done for insertion removal of contact lenses. They will be trained how to place on the secondary magnet spectacles to sit in the correct position on their face. If the participant is able to successfully demonstrate the ability to do this, only then will the magnet device be dispensed home with the patient (see exception* below). During each 1-week during the extended trial, the participant will be advised (instructional sheet sent with the participant) to wear the device as much as they would like up to 8 hours per day in the case of ptosis and 24 hours per day for lagophthalmos so long as comfort remains 5 or better (see participant instructions). Participants will be asked to document their wear time and assess their comfort on a 10-pt scale (10 being best) on a regular (min. daily) basis. For lagophthalmos, the device ideally will be worn 24 hours/day. For ptosis, the magnet glasses will be removed at night, and the lid magnet will remain attached to the eyelid. The participant may shower/wash face with the lid magnet on as the Tegaderm is not critically bothered by water and the magnet is encased in PDMS. They will be advised not to submerge the device (i.e. swim with the device on). Lid magnets will be removed and applied as they start to become detached (typically 2-3 days). If self-assessed comfort is worse than 5/10 or if the intervention fails (eg. stops working or falls off and cannot be reapplied) the participant will be instructed to contact the PI directly. The PI will advise if the device should be removed, and will come to MEEI or Schepens within 24 hours of the complication to evaluate the problem. If there is a problem requiring immediate attention, the participant will be advised to seek attention in the MEEI EW. **AT A 1-WEEK FOLLOW-UP** study appointment we will repeat visual acuity, slit lamp, rating instruments and video recording. **SAFETY CUTOFFS:** The participant's study status will change to suspended and an adverse event reported to the IRB with any of the following findings at the follow-up or any emergency visit: Any broken skin, decrease in visual acuity more than 2 lines, worsening of corneal rating of more than 1.5 points or other ocular surface ratings more than 2 points, and comfort rating lower than 5/10 (or 50cm on the 100cm visual analog scale). The extended trial of the magnet device may be renewed 3 times (for a total of 1 month with weekly visits) as long as the above mentioned criteria continue to be met. If still safe/effective at 1 month, the participant will be given the option to take the device home for an additional 1 month. The device trial/study ends after 8-weeks (4 weekly trials followed by a 1-month trial) or with failure/complication or voluntary withdrawal. If the device is successful over the duration of the study and the participant would like to continue wearing it, a clinical decision will be made as to if and for how long per day it should be worn. This is justified when there appears to be no other equivalent treatments which may be substituted. It would not be ethical to retract the device from a participant if it is working and there is no other comparable option. In such cases, the participant will return 1 month later for an additional follow-up evaluation prior to turning the maintenance of their care over to the neuro-ophthalmology, oculoplastics, or vision rehabilitation service. Their specialist will continue to monitor for complications after the study if the patient keeps the device. The study will end when 25 participants in each group have completed the study (~2yrs). **EXCEPTION* TO TRAINING REQUIREMENT:** If the participant is unable to apply and remove the device themselves (physical or cognitive limitations) and/or they have cognitive impairment (MMSE 20-23), they may still participate in an extended 1-week trial if the following criteria are met: 1) a caregiver is able to be trained to apply/remove the device, 2) The primary caregiver assures 24-hour supervision (see form on the last page of the "instructions for use document"), 3) The cognitively impaired participant (or participant who cannot apply the device themselves) agrees to attend daily study visits for the first

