13) Sample size and statistical power - A sample size or power calculation should be performed. This calculation is used to estimate the number of subjects required to answer your primary study hypothesis with an accepted power. Conversely, it also allows you to estimate what power can be achieved with a limited number of participants. This number is calculated by specifying the magnitude of the effects that are expected (i.e. informed and clinically significant), variability of the measurements and the acceptable degree of type I and II errors. You need to specify the assumptions made for the calculation. It is recommended that you consult with a statistician for this section. Also keep in mind the estimated recruitment rate and whether you need to adjust for anticipated non-responders and losses to follow up.

RESPONSE: The primary hypothesis is that externally mounted magnet systems will have a good safety profile and will be feasible for home use therefore we will report the proportion of participants who have a safety issue and complete the trial. As this outcome is based on summary statistics and not comparisons between groups, a power calculation is not appropriate. Sample size was selected based on providing an as-broad-as-possible but feasible (within the time of the study) assessment of safety and feasibility. The sample size calculation for the secondary within subject comparison between devices is estimated at 10 for the ptosis group, using preliminary unpublished data for cranial nerve III palsy at Spaulding (n=7; efficacy for opening (mm) magnet vs. crutch was borderline with 7 participants p=0.08, and comfort had reached significance, p=0.05). A power calculation is not possible for the lagophthalmos group as preliminary data are only available for 3 participants. Power calculations for the secondary analysis will be re-evaluated during data collection.

14) Statistical methods - The statistical methods used for the study objectives/hypotheses (e.g. t-test, chi-squared, multivariate modeling) must be sufficiently detailed. If conducting a randomized controlled study, you should state whether methods will include an “intention to treat” (ITT) analysis, per protocol analysis, or both. An ITT analysis is preferred as it compares all subjects in the

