groups to which they were originally randomly assigned (despite withdrawal, treatment failure or cross-over). Consultation with a statistician is strongly recommended. [See Harvard Catalyst Statistical Consulting for more information.](#)

RESPONSE: Descriptive statistics will be calculated including a mean rating scale value for skin, corneal integrity, and visual acuity (logmar). A repeated-measures ANOVA will be used to determine if there is any change across visits/measurements. The completeness of opening and closing with and without the magnet and with the other devices will be compared using paired t-tests. As this is not a randomized design, ITT will not be used.

DATA SAFETY MONITORING PLAN (DSMP)

Complete question 15 **OR** 16 depending on the risk of the study. If your study is submitted as minimal risk and determined by the HSC to be more than minimal risk you will be asked to complete question 16 during the review process.

15) If the research is **no more than minimal risk**, please describe any provisions in place to ensure the safety of participants and the validity and integrity of data. If safety monitoring will occur a safety monitoring plan may include elements such as: parameters for safety review, the frequency in which safety review will occur, the person(s) responsible for safety review, and the plan (including the person(s) responsible) for reporting adverse events, protocol deviations, or noncompliance to the HSC and others (where applicable). Data monitoring may include the specific elements that will be reviewed (e.g., informed consent documentation, verification of the accuracy of data), the frequency of data monitoring, and the person(s) responsible.

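### The acuity part of the Section 4a safety definition is a group mean, which can be met while up to about a third of participants have a loss the protocol counts as an adverse event

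*Combined protocol and SAP*

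**What the plan says.** Section 4a (Primary Hypothesis) states that the devices will have a "good safety profile defined as a mean decrease in visual acuity 1 line or less", together with a skin-integrity criterion and a limit of two grades on worsening of keratitis. The word mean is attached to acuity only. Section 4a names no visit and no analysis set.

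Section 7a (Primary Outcome) lists change in acuity and also the number of adverse events, "defined as incidents which require temporary or permanent suspension of the participant's involvement". It continues: "These include any broken skin, decrease in visual acuity more than 2 lines". The list goes on to corneal and other ocular surface worsening and to a comfort rating below 5/10.

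The safety cutoffs in Section 8 apply the same thresholds to each participant: "The participant's study status will change to suspended and an adverse event reported to the IRB with any of the following findings". The findings begin "Any broken skin, decrease in visual acuity more than 2 lines, worsening of corneal rating of more than 1.5 points".

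Section 13 restates the primary hypothesis as a good safety profile and says that "we will report the proportion of participants who have a safety issue and complete the trial". It gives no interval, no acceptable level, and no statement of how the proportion relates to the three 4a criteria. Section 14 plans descriptive means, including acuity in logMAR, a repeated-measures ANOVA across visits, and paired t-tests for opening and closing. It adds no interval for the safety proportion.

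**The concern.** Safety with home use is Aim 1, and the Background says this would be the first study to send participants home with the device. The harm of interest is a clear loss of vision in a few people, not a small shift shared by all. A mean averages those few with everyone else. The only stated acuity criterion for a good safety profile could therefore be met while a sizeable share of participants had a loss that the protocol itself treats as serious enough to suspend them. What is at stake is the conclusion drawn on the primary question, not whether individual events are noticed.

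**Working it through.** **Inputs from the protocol.** Group size 25 (Section 8, opening). Mean acuity limit 1 line (Section 4a). Individual cutoff, a loss of more than 2 lines (Sections 7a and 8). Section 13 gives no power calculation for the primary outcome, so there is no planned figure to reproduce.

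**Assumptions.** The protocol gives no expected loss or event rate. I take losses of 3, 5 and 10 lines; 3 is the smallest whole-line loss past the cutoff. The remaining participants are unchanged, lose 0.5 line on average, or gain 0.5 line on average. Intervals are two-sided 95%.

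**Step 1. How many losses the mean allows.** If m of 25 participants each lose k lines and the others lose b lines on average, the mean loss is

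(m × k + b × (25 − m)) / 25.

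The largest m that keeps this at 1 or below, with the resulting mean in brackets:

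| Lines lost, k | Others unchanged (b = 0) | Others lose 0.5 (b = 0.5) | Others gain 0.5 (b = −0.5) |
|---|---|---|---|
| 3 | 8 (0.96) | 5 (1.00) | 10 (0.90) |
| 5 | 5 (1.00) | 2 (0.86) | 6 (0.82) |
| 10 | 2 (0.80) | 1 (0.88) | 3 (0.76) |

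For example, 8 × 3 / 25 = 0.96 meets the criterion and 9 × 3 / 25 = 1.08 does not. Also, 2 × 10 / 25 = 0.80 meets it and 3 × 10 / 25 = 1.20 does not. With the others unchanged, the affected share can be as large as 1/k, so the same holds for both groups together: 16 × 3 / 50 = 0.96.

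**Step 2. What the proportion would show.** For 8 of 25, the proportion is 32%. The exact (Clopper-Pearson) limits are the 2.5% point of Beta(8, 18) and the 97.5% point of Beta(9, 17), that is 14.9% and 53.5%.

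**Step 3. What a group of 25 can establish.** With no events, the exact upper limit is 1 − 0.025^(1/n), which is 13.7% for n = 25 and 7.1% for n = 50. With 1 or 2 events in 25 it is 20.4% or 26.0%.

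**The case against.** The strongest reply is that a group criterion and an individual suspension rule do different jobs and can coexist. Adverse event counts are themselves listed under Primary Outcome, each loss of more than 2 lines leads to suspension and a report to the IRB, and visits are weekly in the first month. All of that stands: the harm would not go unseen. It does not repair the 4a definition, because the counts carry no rule that bears on it.

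The scenarios also show what is possible, not what is likely. Further, 4a requires the skin and keratitis criteria too. The keratitis limit reads most naturally as per participant, so a vision loss with corneal worsening beyond two grades would fail 4a by that route. This limits the point to acuity. Nothing in the text says that every acuity loss would come with such a failure.

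Three stronger readings are tempting but not supported.

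- A reader might infer that the plan gives two conflicting verdicts on one hypothesis. It does not. The Section 13 proportion has no limit, so it yields no verdict that could contradict 4a, and Section 13 ties it to the hypothesis by name. What is missing is an interval and a decision rule.
- A reader might infer that suspended participants drop out of the mean, so that any number of losses would pass. No section says so. Acuity is measured at the same follow-up visits at which the cutoffs are applied.
- A reader might infer from "The study will end when 25 participants in each group have completed the study" that suspended participants are replaced and each group grows beyond 25. Section 8 also sets enrolment at 25 per group and says that a participant's study ends at 8 weeks or with a complication or withdrawal, so completion can include those who stopped for harm. The denominator does deserve a plain statement, since Section 14 rules out intention-to-treat and names no other set.

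Finally, this is a small, uncontrolled feasibility study, and a fixed pass limit is not obligatory. That is correct; an interval and a named denominator need neither a limit nor a power calculation.

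**Conclusion.** The point holds for acuity. A mean loss of 1 line or less does not limit individual loss to a low rate. In a group of 25 with the others unchanged, it is compatible with 8 participants (32%) losing 3 lines or 2 participants losing 10 lines. If the others lose 0.5 line on average, the figures are 5 and 1; if they gain 0.5 line, 10 and 3. The loss sizes are assumptions, and the skin and keratitis criteria must be met as well, so this is a statement about what the acuity criterion permits, not a forecast. Section 13 reports a relevant proportion under the same hypothesis but gives it no interval and no bearing on 4a. The definition should be changed before the data are analysed.

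**What to change.** In Sections 4a and 13, make the acuity criterion the number and proportion in each group who lose more than 2 lines at any follow-up or emergency visit, with an exact 95% interval. Count every participant who took the device home, including those suspended or withdrawn, because home use is what Aim 1 asks about. Show all fitted participants separately. Report the proportion with any Section 7a safety event in the same way, with comfort-only events shown apart so that they do not obscure harm to the eye or skin. Keep mean acuity as a description.

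Whether to set a pass limit, and where, is the investigator's clinical choice. It should be made in advance, knowing that even 0 of 25 leaves an upper limit of 13.7%. If fewer than 25 in a group take the device home, that limit is higher.

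The cost is in the conclusion: the safety statement becomes less favourable and visibly less certain than one based on a mean. No procedure is added, since acuity is already measured at baseline and repeated at follow-up.

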You should include precise details of the treatment(s)/intervention(s) intended for each group/participant. You should also provide details of any follow-up schedule (i.e. time between visits) and consider how you will monitor participants' adherence with the treatment schedule. You might also describe under which circumstances participants may be withdrawn and how this will occur. A schematic diagram or flow chart may be useful for this section.

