RESPONSE: Twenty-five participants each with either paralytic ptosis or lagophthalmos will be enrolled for a total of 50 participants. The OCRO will assist in pre-identifying potential candidates targeting the practices of Dr.'s [name], [name], and [name]. They will mention the study to them/providing approved recruitment information (flyer and study description page). If OCRO pre-screening misses someone whom the Dr.'s think might be a candidate, they will mention the study and have their clinical staff provide the approved recruitment materials (a flyer and study brochure). A separate appointment will be arranged for the study candidate to return, if they are interested, to speak with the PI about the study and perform informed consent (conducted by the PI or other trained and experienced study personnel). Study visits may occur at MEEI in the Oculoplastics, Neuro-Ophthalmology, or Vision Rehabilitation Clinics, or at Schepens Eye Research Institute in the Lions Exam room booked with the online SERInet scheduling system. If seen at SERI, all data collected will be for research purposes (no clinical component); i.e. there will not be any overlap with their typical Ophthalmological care. If data is collected at MEEI, there may be, in the interest of efficiency, measurements taken clinically which can also be used for research to include visual acuity and slit lamp biomicroscopy. The PI will explain the study as detailed in the "consent" section and administer a pre-consent cognitive screening using the Mini-Mental State Exam (MMSE). If score is 18-23 (maximum of 30) representing mild cognitive impairment (Tombaugh et al 1992), candidates will be asked return with a caregiver (if one is not present). If score is <18, they will not be eligible. After the consent process, participants will complete the VFQ-25 (Mangione, 2001) and the MoCA (Montreal Cognitive Assessment, Nassreddine et. al 2012), have their visual acuity measured, anterior segment evaluation with NaFl and Lissamine Green, and a video recorded of their baseline eyelid function (capturing only the eyes).

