This will be followed by fitting of the experimental magnetic device. A video is recorded for approximately 1 minute to document device performance and a rating instrument (visual analog scale for participant measures and a likert-type 10-pt scale for the examiner) is administered to capture subjective comfort and opinion of efficacy (see rating scales attached). **DEVICE FITTING DETAILS-THE IMMEDIATE TRIAL: FOR PTOSIS**, In order to best fit the MLP we will measure 1) the force (i.e. magnet size) needed to elevate the paralyzed lid; 2) the thickness of the coating on the spectacle magnet needed to allow adequate blinking; 3) the best orientation of the magnets (thru height or thru thickness). Force measurement to open or close the eye lid may be taken by attaching a low force transducer (miniature strain gauge) to the lid(s) with a small piece of IV 3000 medical tape, a 2-3 minute procedure.

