Next, a lid attached magnet array (see photos in manuscript attached) is painlessly applied to the upper lid with the participant's eye closed by placing a small swatch of Tegaderm medical adhesive (3M, St. Paul MN, Smith and Nephew, Canton MA) over the top of the micro-magnet array (a 1-minute procedure). For ptosis the array is only attached to the upper lid and a set of fit-over frames with a larger magnet embedded within the upper eye wire (spectacle magnet), which can be worn over the participants own glasses if needed, will be placed on and adjusted to the appropriate position. This secondary spectacle mounted magnet activates the ptosis system, providing the force to lift the lid. The spectacle magnet must be encased in plastic, and if the coating is too thin, the patient will not be able to blink properly. To determine the best coating thickness we will test 10 different coating thicknesses, done with 1mm plastic inserts which can be stacked. The video is recorded and rating instruments completed. This process is then repeated for lid magnets having a slightly modified polarity (thru height compared to the standard thru thickness). We will also test 4 different orientations of the spectacle magnet to determine the best fitting. **FOR LAGOPHTHALMOS** (failure of eye closure, e.g. facial palsy) the participant will first be fitted with a predicate device, an external lid weight, applied with double-sided "blink-eze" adhesive (supplied by the distributor with the product) and the video recording and rating instruments completed. Then this will be removed and lid magnet arrays identical (or very similar) to those described for ptosis will be applied to the upper and lower lids. The weight of the upper magnet will pull the eyelid down in a similar manner as the gold lid weight. (Townsend, 1992) The magnet on the lower lid will promote a more complete blink as the two magnet arrays draw towards one-another. A secondary

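### Magnet versus ptosis crutch is a planned paired comparison, but the ptosis steps in Section 8 include no crutch measurement; the device order in lagophthalmos also needs clarifying against Section 9

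*Combined protocol and SAP*

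**What the plan says.** All references are to the combined protocol and SAP.

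**Where the crutch comparison is planned**
- Section 7b (secondary outcomes) compares the magnet's video results with no device, with the other eye if normal, and "relative to the ptosis crutch or external lid weights. The same paired comparisons will be performed for the clinician and participant rating scale data".
- Section 10 (study specific procedures) lists the comparison of opening and closing with the magnet against the crutch or lid weights, and efficacy ratings by clinician and participant.
- Section 13 (sample size) estimates 10 ptosis participants for the within-subject device comparison, citing magnet-versus-crutch pilot data from 7 people.
- Section 14 (statistical methods) applies paired t-tests to opening and closing, with the other devices included.

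**What Section 8 (study procedures) describes**
- Its prompt asks the author to "clearly and comprehensively describe exactly what will happen to participants once they are enrolled in your study" and adds: "You should include precise details of the treatment(s)/intervention(s) intended for each group/participant".
- Numbers: "Twenty-five participants each with either paralytic ptosis or lagophthalmos will be enrolled for a total of 50 participants".
- After the baseline video: "This will be followed by fitting of the experimental magnetic device".
- Ptosis: "The video is recorded and rating instruments completed. This process is then repeated for lid magnets having a slightly modified polarity". Coating thicknesses and spectacle-magnet orientations are also tested.
- Lagophthalmos: "the participant will first be fitted with a predicate device, an external lid weight", with video and ratings. "Then this will be removed and lid magnet arrays identical (or very similar) to those described for ptosis will be applied".

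**Order.** Section 9 (randomization) answers in one unpunctuated sentence that runs the absence of randomization together with the use of counterbalancing, giving small sample size as the reason. It does not say what would be counterbalanced.

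**The concern.** A paired analysis needs both measurements on the same person. If site staff work from Section 8, no ptosis participant is filmed or rated wearing a crutch, and those recordings cannot be recovered at analysis. The ptosis half of the third comparison in Section 7b would then have no data, and neither would the one device comparison that was sized.

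The lagophthalmos comparison raises a smaller issue. If every participant is tested with the lid weight first and the magnets second, then learning, fatigue, eyelid irritation or a shift in how the rating scale is used between the two fittings would be counted as a device difference. Section 9 appears to promise a safeguard, but does not say whether it covers this order.

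**Working it through.** **1. The plan's own figure (10 in Section 13).** The inputs are n=7, p=0.08 for opening and p=0.05 for comfort. The plan gives no mean difference, SD, alpha, sidedness or power, so those used here are assumptions.
- Opening, two-sided p=0.08 on 6 df: t = 2.104, so d = 2.104/√7 = 0.795.
- Normal approximation n = ((z for alpha + z for power)/d)². Two-sided 5%, 80% power: ((1.960+0.842)/0.795)² = 12.4, so 13. The non-central t gives 15.
- One-sided 5%, 80% power: ((1.645+0.842)/0.795)² = 9.8, so 10. The non-central t gives 12.
- Comfort, two-sided p=0.05: d = 0.925. Two-sided 5%, 80% power: ((1.960+0.842)/0.925)² = 9.2, so 10. The non-central t gives 12.

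Some standard choices return 10 and others do not, so the figure can be neither confirmed nor called wrong. The present point does not depend on it.

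**2. Crutch measurements, section by section**

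| Section | Crutch |
|---|---|
| 7b | Planned, for video and ratings |
| 8, ptosis steps | No fitting, video or rating |
| 8, 20-minute and extended trials | Magnet device only |
| 10 | Comparison listed; no step, timing or order |
| 13 | Basis of the estimate of 10 |
| 14 | Covered by the reference to other devices |

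The Section 8 response never mentions a crutch. Brevity is an unlikely explanation, because the same response fits, films and rates the lid weight in lagophthalmos. Pairs obtained by following Section 8 alone: 0 of 25 planned ptosis participants, against the 10 estimated.

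**3. Order in lagophthalmos (illustration only).** The documents give no order effect, so the shifts below are assumed. Suppose there is no true device difference, all 25 participants supply a pair, paired differences are normal, and being tested second moves the paired difference by s SDs.
- Fixed order: the bias is s. The paired t statistic has 24 df and non-centrality s√25 = 5s. The two-sided 5% critical value is 2.064.
- Orders split 13/12: the bias is s × (13−12)/25 = s/25. Rejection rates are by simulation.

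| Assumed s | Non-centrality, fixed order | False positives, fixed order | Bias, 13/12 split (SD) | False positives, 13/12 split |
|---|---|---|---|---|
| 0 | 0 | 5% | 0 | 5% |
| 0.05 | 0.25 | 5.7% | 0.002 | at most 5% |
| 0.1 | 0.5 | 7.7% | 0.004 | at most 5% |
| 0.2 | 1.0 | 16% | 0.008 | 4.6% |
| 0.3 | 1.5 | 30% | 0.012 | 4.0% |
| 0.5 | 2.5 | 67% | 0.020 | 3.0% |

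With the split orders the rate drops below 5% because the order effect adds to the spread of the differences without moving their mean much.

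**The case against.** **Crutch.** No section says a crutch will not be used. Section 10 answers a request to list all research procedures and names the comparison, so the measurement is called for. The attached rating forms, manuscript and participant instructions, and the study checklist mentioned in the monitoring plan, are not available to us and could carry the step. This stands as a limit: a reader might infer that the crutch data will certainly be lost, and the documents do not support that. They show only that Section 8 gives no step and that Section 10 gives no timing or method. Section 8 still has to agree with Sections 7b, 10 and 13.

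**Order.** A reader might infer that Sections 8 and 9 flatly contradict each other. That is not proven, for two reasons. The Section 9 sentence most naturally says that counterbalancing will be used, but it could mean that neither randomization nor counterbalancing is used, and the conflict then disappears. Even on the natural reading it names no object, and could refer to the coating thicknesses, polarities or magnet orientations in Section 8. What stands is that Section 9 is unclear and that Section 8 fixes the order.

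**Error rates.** The larger rates could be taken as the plan's actual false-positive rate. They are not: they follow from assumed shifts, and small shifts do little harm. Section 14 names paired t-tests only for opening and closing; for ratings, where order effects may be more plausible, it names no test of the device comparison.

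**Reach.** The study is aimed at safety and feasibility, and no lagophthalmos comparison was sized. That stands and limits the severity.

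**Conclusion.** The crutch gap holds with high confidence as a statement about Section 8 as written: a planned paired comparison, and the only one with a sample size, has no measurement step. Its size is 0 of 25 possible pairs if Section 8 is followed alone. That count assumes that no unseen form or checklist supplies the step.

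The order point holds with moderate confidence. The fixed lid-weight-first order confounds device with order completely, whatever Section 9 means. Whether it also breaks a commitment in Section 9 cannot be settled from the sentence as it stands. The numerical effect is unknown, and the rates shown are illustrations.

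The primary safety and feasibility outcome and the Section 4b hypotheses (with versus without the device, and comfort) are unaffected. The change should be made, but the main conclusions of the study do not depend on it.

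**What to change.** 1. **Crutch.** Reconcile the sections in one of two ways.
   - Add to the Section 8 ptosis steps the crutch video and ratings that Sections 7b and 10 already call for, with their timing. This costs one fitting, one video and one set of ratings per ptosis participant, already foreseen in Section 10.
   - Or remove the crutch comparison from Sections 7b, 10 and 13, so that the other devices in Section 14 mean the lid weight only. This costs deletions, and the estimate of 10 goes with it.
2. **Order.** Repair the Section 9 sentence and state what is counterbalanced.
   - If it covers device order, have Section 8 alternate lid weight and magnets, about 13 participants in one order and 12 in the other. No extra recordings are needed.
   - If the fixed order is intended, say so in Section 9, and state in the report that device and order cannot be separated.

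Neither change needs more participants. Both should be made before further participants are fitted, because missing crutch recordings and an unvaried order cannot be repaired at analysis.
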